6.7.1. Ocular Symptoms Questionnaire

The Investigator will query the subject for the severity of the ocular symptoms in the study eye as indicated in [Appendix 2](#). This questionnaire should be conducted before other ocular assessments are performed by the Investigator or delegate.

6.7.2. Ocular Pain Measurement Rating Scales

This rating scale should be conducted before other ocular assessments are performed by the Investigator or delegate. Refer to [Appendix 3](#) for details.

6.7.3. Ocular Injury - Physician Assessment

The Investigator will assess the injury in the study eye at

Refer to [Appendix 8](#) for the assessment scale and criteria.

6.7.4. Slit Lamp Examination

Slit lamp biomicroscopy (without pupil dilation) will be performed during the study on both the study eye treated with investigational product and fellow eye. Observations for the slit lamp biomicroscopy will be graded as detailed in [Appendix 5](#).

6.7.5. Measuring the Epithelial Defect and Photography Assessments

The epithelial defect size will be recorded to assess eligibility PRIOR to Day 1 and randomization on Day 1 then at all following visits, as indicated in [Table 1](#): Schedule of Assessments. The cornea will be stained with **fluorescein** prior to measurement.

The size of the PED will be measured:

■ [REDACTED]

■ [REDACTED]

■ [REDACTED]

To ensure the corneal epithelium remains undisturbed after randomization, [REDACTED] [REDACTED] Assessment and measurement of the defect size will be done [REDACTED] using fluorescein. [REDACTED]

One drop of lubricant can be used to moisten a fluorescein strip, shaken once, then touched to either the tear film or the inferior fornix. After two to three blinks, photographs can be taken. [REDACTED]

Extreme care must be taken to avoid physical disruption of the healing epithelium.

[REDACTED]
[REDACTED] photographs may be taken [REDACTED], *i.e.*, focused and with the entire defect in view, are achieved. Refer to [Appendix 6](#) and [Appendix 7](#) for details.

A separate User's Manual will provide additional instructions on the slit lamp photography to those site personnel responsible for taking the digital images and measuring the PED. All users must also have training on the instructions prior to undertaking any photographs for this study.

[REDACTED]

6.7.6. Visual Acuity

Visual acuity is to be performed in the same manner at each scheduled assessment. Refer to [Appendix 4](#).

[REDACTED]
[REDACTED]
[REDACTED]
[REDACTED]
[REDACTED]

6.7.7. Ophthalmoscopy

If possible, an ophthalmoscopic assessment –

[REDACTED]
[REDACTED] will be performed with the eye dilated when re-epithelialization occurs or when the subject exits the Treatment Period with an unhealed PED.

[REDACTED]
[REDACTED]

6.7.8. Intraocular Pressure

Intraocular pressure (IOP) will be assessed in both the study eye and fellow eye only on the days shown in [Table 1](#): Schedule of Assessments.

[REDACTED]
[REDACTED]
[REDACTED]

A final IOP measurement will be taken when the subject exits the study.

The method used to measure IOP, whilst not standardized across study sites, MUST be kept the same for each individual subject within a study site.

[REDACTED]

7. INVESTIGATIONAL PRODUCT

7.1. Description of the Investigational Product

The investigational product used in the study will be NEXAGON® [REDACTED] (NEXAGON) formulated at [REDACTED] and Vehicle 0.0 mg/mL (0%).

NEXAGON is a [REDACTED] gel for topical ophthalmic application. The investigational product is formulated with sterile, [REDACTED]

[REDACTED] All vials are identical in appearance and the vial labels will not identify the contents, *i.e.*, the treatment allocated to a subject will be masked to both the site and other personnel working on this study. Vials will be labeled with codes and it will not be possible to know what the contents of the vials are, unless there is a medical emergency requiring unmasking (refer to [Section 7.8](#)).

7.2. Dosage

Each investigational product and Vehicle dose application to the study eye will comprise of [REDACTED]

No topical ocular drops or ointment standard of care treatment will be permitted [REDACTED] following investigational product administration.

Investigational product will be applied on [REDACTED]

7.3. Packaging and Labeling

The contents of the investigational product label will be in accordance with all applicable regulatory requirements. Each Investigator will be supplied with sufficient supplies to conduct the trial. Additional study kits treatment packs will be supplied as needed to the site.

The investigational product will be provided to the site packaged in tamper-evident masked study kits. Investigational product is double-masked with neither the Investigator or subject knowing which treatment arm has been allocated.

[REDACTED] The labels on the primary and secondary containers will not identify the contents.

[REDACTED] Refer to [Section 7.7 Treatment Assignment](#) for further details.

7.4. Investigational Product Storage, Handling and Administration

Investigational product will be dispatched to a site only after receipt of required documents in accordance with all regulatory requirements and Amber procedures.

Only subjects enrolled in the study may receive investigational product, in accordance with all regulatory requirements. Investigational product must be dispensed or administered according to procedures described herein.

7.4.1. Investigational Product Storage

Investigational product study kits should be maintained [REDACTED] and must be stored in a secure area, with access limited to the Investigator and authorized site staff.

Each site will be dispatched a pre-determined supply of investigational product study kits and ancillary cartons. Additional study kits and ancillary cartons of investigational product will be supplied as needed.

7.4.2. Investigational Product Dispensing – Masked Study Kits

Three treatment groups will be evaluated in this study [REDACTED]

- GROUP A – [REDACTED]
- GROUP B – [REDACTED]
- GROUP C – Vehicle (0%)

Only authorized site staff will be able to dispense and supply investigational product to the study subject. No special safety requirements are required prior to handling the investigational product.

The designee will remove the assigned study kit - the lowest Kit Number in their inventory - from the refrigerator and write the Subject Identifier (ID) on the outer study kit label. The designee must also confirm that the tamper-evident label which seals the study kit is still intact. If the tamper-evident label is voided in any way the kit should be set-aside in the secure storage area and not used. The Study

Monitor should be contacted and a replacement study kit can be organized through the nominated unmasked study statistician.

An intact study kit will be opened on Day 1 of the study, the day of randomization. The designee should remove the vial labelled Day 1 and [REDACTED]

[REDACTED] and to ensure that there is no visible damage to the container. If the investigational product container appears to be compromised, it should not be used, but instead returned [REDACTED]

Once checked and confirmed as being in a good condition, the appropriate vial [REDACTED]

[REDACTED]

[REDACTED]

[REDACTED]

[REDACTED]

[REDACTED]

[REDACTED]

7.4.3. Investigational Product Dispensing – Open-Label Ancillary Cartons

For subjects requiring a [REDACTED]

[REDACTED]

[REDACTED]

[REDACTED]

[REDACTED]

7.4.4. Investigational Product Administration

No topical ocular drops or ointments standard of care treatment should be applied [REDACTED] investigational product administration.

When the subject is due to receive investigational product, the vial should be [REDACTED]

[REDACTED]

A series of horizontal black bars of varying lengths, each ending in a white rectangular gap. The bars are arranged vertically, with the gaps at the end of each bar creating a staggered effect. The lengths of the bars decrease from top to bottom.

Further details on presentation, storage, administration and accountability will be provided in the study Pharmacy Manual.

7.5. Product Accountability

The Investigator is responsible for investigational product accountability, reconciliation and record maintenance. In accordance with all applicable regulatory requirements, the Investigator or designated staff must maintain investigational product accountability records throughout the course of the study. The responsible person(s) will document the amount of investigational product received from and returned to Amber, the amount administered to subjects, and the amounts destroyed at the site.

7.6. Assigning the Subject Identifier (Subject ID)

Upon signing the informed consent form, each subject will be allocated a unique Subject ID, consisting of a 3-digit study site number and then a 3-digit sequential number corresponding to the order in which subjects are screened at that site, *e.g.*, 001, 002, 003, *etc.*

The unique Subject ID assigned will be retained by that subject for the duration of their participation in the study.

7.7. Treatment Assignment

Subjects will be assigned to one [REDACTED] treatment arms in accordance with the randomization schedule. [REDACTED]

[REDACTED]

[REDACTED]

[REDACTED]

[REDACTED]

[REDACTED]

7.8. Unmasking

The Investigator may unmask a subject's treatment assignment only in the case of an emergency when knowledge of the investigational product is essential for the clinical management or welfare of the subject. [REDACTED]

[REDACTED]

[REDACTED]

If a drug-related serious adverse event (SAE; as defined in [Section 9.2: "Definition of an SAE"](#)) is reported, the Medical Monitor may unmask the treatment assignment for the individual subject. If an expedited regulatory report to one or more regulatory agencies is required, the report will identify the subject's treatment assignment. When applicable, a copy of the regulatory report may be sent to the Investigator in accordance with relevant regulations, Sponsor policy or both.

8. SUBJECT COMPLETION AND WITHDRAWAL

8.1. Subject Completion

In order to be considered a study completer, subjects must meet the following TWO criteria:

1. Complete the masked Treatment Period until either of the following
 - a. Re-epithelialization
 - b. Completion of [REDACTED]
2. Enter and complete the [REDACTED] Post-healing Follow-up Phase (following re-epithelialization during [REDACTED] Double Masked Treatment Phase or re-epithelialization during open-label section of the study*).

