8.1.1. Subject Premature Withdrawal from Study

A subject who is administered investigational product, but who does not complete the study, as defined in [Section 8.1](#), has prematurely discontinued. Prematurely discontinued subjects will not be replaced.

A subject may voluntarily discontinue participation in this study at any time. The Investigator may also, at his/her discretion, discontinue the subject from participating in this study at any time for safety reasons.

In addition, subjects WILL be withdrawn from the study, in consultation with the Medical Monitor and the Investigator, if any of the following criteria are met:

- A subject is significantly non-compliant with the requirements of the protocol.
- A subject becomes pregnant (NOTE: the pregnancy will be followed up to term for safety follow-up. Relevant safety information collected after the study has completed will be reported as supplemental information).
- [REDACTED]
- Sponsor discontinues the study.

Premature withdrawal from the study MAY occur if:

- A subject is treated with a prohibited medication. This decision will be made by the Medical Monitor in conjunction with the Investigator as to whether premature withdrawal is warranted.
- The condition of the study eye worsens in the opinion of the Investigator and alternative rescue treatment is required.

Subjects who meet the criteria for premature withdrawal, during the Treatment Period will have the [REDACTED] / Exit Visit performed.

Subjects who meet the criteria for premature withdrawal, during the Post-healing Follow-up Period will complete all the ophthalmic assessments of the visit where the premature withdrawal criterion was identified, if possible.

All subjects who exit the study prematurely will have a safety follow-up visit (unscheduled visit) or telephone call scheduled 30 days after their last application of investigational product to assess any AEs/SAEs.

If a subject is prematurely discontinued from participation in the study for any reason, the Investigator must make every effort to locate and perform all evaluations specified above.

Any clinically significant adverse events or clinically significant unfavorable changes in the laboratory tests observed during the discontinuation visit will necessitate that the subject be followed or referred for treatment until satisfactory resolution occurs.

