9.1. Definition of an AE

An AE is any untoward medical occurrence in a subject or clinical investigation subject administered a pharmaceutical product and that does not necessarily have a causal relationship with this treatment. An AE can therefore be any unfavorable and unintended sign (including an abnormal laboratory finding), symptom, or disease temporally associated with the use of an investigational product whether or not related to the investigational product.

AEs will be recorded from the time of first application of the investigational product and until the final visit.

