11.4. Study Discontinuation

Amber has the right to terminate or suspend this study at any time. Reasons for terminating the study may include but are not limited to the following:

- The incidence or severity of adverse events in this or other studies that indicates a potential health hazard to subjects;
- Subject enrollment is unsatisfactory;
- Data recording is repeatedly inaccurate or incomplete, i.e., persistent non-compliance with GCP;
- Large numbers of prematurely discontinued subjects;
- Significant protocol violations (i.e., violation of eligibility criteria, dosing errors, and/or missing data for study endpoint analysis).

Compliance with the following is mandatory: GCP 5.21 (Sponsor: Premature Termination or Suspension of a Trial and GCP 4.12 Investigator: Premature Termination or Suspension of a Trial).

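### Do the completer rules need changing because a subject who attends every visit but never heals is classed as prematurely discontinued?

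*Protocol*

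**What the plan says.** Protocol 8.1 sets the completer rule: "In order to be considered a study completer, subjects must meet the following TWO criteria". The first is to finish the masked Treatment Period, either by healing or by reaching a redacted end point. The second is to enter and finish the post-healing follow-up, after healing in the "Double Masked Treatment Phase or re-epithelialization during open-label section of the study". An asterisk follows those words, and its footnote is not in the public text.

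Protocol 8.1.1 takes everyone else: "A subject who is administered investigational product, but who does not complete the study, as defined in" Section 8.1 is prematurely discontinued and is not replaced. The same section attaches procedures to premature exit. One is general: "All subjects who exit the study prematurely will have a safety follow-up visit (unscheduled visit) or telephone call scheduled 30 days" after the last application. Two depend on the period: "Subjects who meet the criteria for premature withdrawal, during the Treatment Period will have the" exit visit, and "Subjects who meet the criteria for premature withdrawal, during the Post-healing Follow-up Period will complete all the ophthalmic assessments" of the visit at which the withdrawal criterion was found. Neither of these two names the open-label section.

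Protocol 11.4 lists "Large numbers of prematurely discontinued subjects" among the possible reasons for ending the study. Protocol 9.1 says that "AEs will be recorded from the time of first application of the investigational product and until the final visit".

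SAP 9 has its own rule: anyone not discontinued is a completer. It does not define discontinuation or refer to Protocol 8.1. Its list of reasons does not name non-healing but does include a category for other reasons.

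**The concern.** Failing to heal after the masked period and the salvage doses is an expected outcome with its own described route out of the study (synopsis, Protocol 4.1, SAP 3.1). Protocol 6.3 names non-healing as a reason for exit. It is odd for a subject who follows that route to its end to be put with people who walked away. If the SAP counts the same subject as a completer, two analysts could build different disposition tables from the same data.

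The label is also used outside that table. The 30-day contact in 8.1.1 goes to premature exits. Never-healed subjects are the ones who, under Protocol 1.4.2, are offered open-label NEXAGON at the highest concentration, and the incidence of treatment-emergent adverse events is the safety endpoint. If a site regarded their exit as planned, adverse events after that exposure might be missed. The count named in 11.4 would also mix an efficacy outcome with dropout.

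**Working it through.** The documents give no figure to reproduce: the sample size, healing rates, discontinuation rate and allocation ratio are all redacted. The check is to follow one subject through the text: dosed, present at every planned visit, salvage given, never healed.

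1. **Protocol 8.1.** Criterion 1 is met by reaching the end of the masked period. Criterion 2 cannot be met, because the post-healing follow-up starts only when the cornea heals (Protocol 4.1). Unless the footnote says otherwise, the subject is not a completer.

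2. **Protocol 8.1.1.** A dosed non-completer is prematurely discontinued. This is the only definition of premature exit that sites can see in the public text.

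3. **Exit wording elsewhere.** The synopsis, Protocol 4.1 and SAP 3.1 say that the unhealed subject leaves the study. None says that leaving counts as completing it. Protocol 4.1 also uses the word exit for a subject whose epithelium breaks down and who then moves to salvage dosing, so the word is neutral. Only durable healers are described as having finished all visits, which agrees with 8.1.

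4. **SAP 9.** If a planned exit is not a discontinuation, the subject is a completer. If the 8.1.1 definition is carried over, the subject is discontinued under the other-reasons category. Both readings fit the words. The SAP takes precedence over the protocol only on statistical analysis methods (Protocol 10, SAP 1), so it does not alter what sites do under 8.1.1.

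5. **Primary analysis.** SAP 13.1 counts as failures those who leave early and those whose missing data prevent a conclusion. A subject who never healed is a failure by observation. The outcome is a failure under either label, and the change in the estimate is zero.

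6. **Safety contact.** Steps 1 and 2 make the subject a premature exit, so the 30-day contact applies. Separately, the synopsis, Protocol 4.1 and SAP 3.1 provide for adverse events to be assessed in all subjects up to a redacted time after the last application. Salvage subjects have a final healing assessment (Protocol 4.1, SAP 3.1). Pressure and, where relevant, pregnancy are checked at exit (Protocol 6.7.8, 6.3). The recording window in 9.1 does not prevent a 30-day visit from being the final visit.

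7. **Termination list.** Protocol 11.4 gives examples, says they are not exhaustive and sets no count. Nothing follows automatically from how never-healed subjects are classified.

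8. **Disposition.** Protocol 10.2.6 and SAP 9 already report completion and withdrawal for the main study and for the open-label section. Healing is tabulated as the primary outcome.

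**The case for a change.** The strongest case for acting is that step 6 works only if sites apply a counter-intuitive definition literally. A coordinator who sees a subject leave on schedule may not think of 8.1.1. The sentences on exit visits omit the open-label section, so the 30-day contact is the only one that 8.1.1 itself visibly provides for these subjects. If the missing footnote exempts them from premature status, the 8.1.1 wording no longer reaches them, and what remains is the general adverse-event window, whose length is redacted. Enrolment is also tied to the number who complete the study (Protocol 4.1, 5.1), so the label could affect how long recruitment runs.

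Part of this stands. The two documents do not share a completer definition, and the public text cannot show that every exit is followed for 30 days. But it cannot show a gap either: that would need either a site setting aside the protocol's only definition, or a footnote that exempts these subjects together with a general window shorter than 30 days. On enrolment, leaving never-healed subjects out of the completer count would lengthen recruitment, up to the stated maximum. With both the target and the maximum redacted, no effect can be shown. Any percentage of subjects affected would rest wholly on assumed healing and dropout rates.

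**Conclusion.** No change to the plan is called for. On the visible text, Protocol 8.1 and 8.1.1 class a fully attending, never-healed subject as prematurely discontinued, while SAP 9 uses a looser rule with an undefined term. This is a gap in wording that analysts can fill sensibly: check the footnote in the full protocol, apply one meaning of completion throughout, and make unhealed subjects who finished all visits distinguishable from dropouts in the disposition output. Anyone who counts them as completers should note that the 30-day contact in 8.1.1 is tied to premature exit.

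The effect on the primary estimate is none. No effect on enrolment or on safety collection is shown. The conclusion assumes that sites follow 8.1.1 as written and that the unseen footnote does not remove these subjects from its reach. If it does, the length of the general adverse-event window, given in the unredacted documents, would decide whether anything is lost.

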8.1.1. Subject Premature Withdrawal from Study

A subject who is administered investigational product, but who does not complete the study, as defined in [Section 8.1](#), has prematurely discontinued. Prematurely discontinued subjects will not be replaced.

A subject may voluntarily discontinue participation in this study at any time. The Investigator may also, at his/her discretion, discontinue the subject from participating in this study at any time for safety reasons.

In addition, subjects WILL be withdrawn from the study, in consultation with the Medical Monitor and the Investigator, if any of the following criteria are met:

- A subject is significantly non-compliant with the requirements of the protocol.
- A subject becomes pregnant (NOTE: the pregnancy will be followed up to term for safety follow-up. Relevant safety information collected after the study has completed will be reported as supplemental information).
- [REDACTED]
- Sponsor discontinues the study.

Premature withdrawal from the study MAY occur if:

- A subject is treated with a prohibited medication. This decision will be made by the Medical Monitor in conjunction with the Investigator as to whether premature withdrawal is warranted.
- The condition of the study eye worsens in the opinion of the Investigator and alternative rescue treatment is required.

Subjects who meet the criteria for premature withdrawal, during the Treatment Period will have the [REDACTED] / Exit Visit performed.

Subjects who meet the criteria for premature withdrawal, during the Post-healing Follow-up Period will complete all the ophthalmic assessments of the visit where the premature withdrawal criterion was identified, if possible.

All subjects who exit the study prematurely will have a safety follow-up visit (unscheduled visit) or telephone call scheduled 30 days after their last application of investigational product to assess any AEs/SAEs.

If a subject is prematurely discontinued from participation in the study for any reason, the Investigator must make every effort to locate and perform all evaluations specified above.

Any clinically significant adverse events or clinically significant unfavorable changes in the laboratory tests observed during the discontinuation visit will necessitate that the subject be followed or referred for treatment until satisfactory resolution occurs.

In the event that a subject is prematurely discontinued from the study at any time due to an adverse event (AE) (as defined in [Section 9.1](#)) or SAE (as defined in [Section 9.2](#)), the procedures stated in Section 9 must be followed.

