Study Periods/Duration	
The study will comprise a [REDACTED] Treatment Period and a Post-healing Follow-up Period of [REDACTED] both of which are double-masked.
 
Once determined to be eligible, subjects will be randomized to receive either NEXAGON [REDACTED] or NEXAGON [REDACTED] or Vehicle in a [REDACTED] ratio respectively. Investigational product will be applied [REDACTED]
 
[REDACTED] during the Treatment Period:
 
[REDACTED] [REDACTED] [REDACTED] [REDACTED]
 
However, if by [REDACTED] of the Treatment Period the cornea has not fully re-epithelialized, irrespective of the investigational product assignment at randomization, subjects will enter the open-label section of the study and will receive [REDACTED] applications of NEXAGON [REDACTED] NEXAGON [REDACTED] will be applied [REDACTED]. Subjects receiving salvage therapy will be followed from the first salvage dose application to determine if re-epithelialization occurs [REDACTED].
 
For each subject, the [REDACTED] masked Treatment Period will end when EITHER, corneal re-epithelialization is [REDACTED] recorded following up to a maximum of [REDACTED] applications of investigational product OR subjects enter the open-label section of the study as a result of an unhealed PED [REDACTED].
 
Those subjects who achieve re-epithelialization will immediately begin the [REDACTED] Post-Healing Follow-up Period. No further investigational product will be applied. The aim of the post epithelialization follow-up period is to assess the durability of the epithelium.
 
For those subjects that achieve re-epithelialization but epithelialization is NOT sustained during the [REDACTED] Post-healing Follow-up Period, the subject will become eligible to receive the salvage dose(s) of NEXAGON [REDACTED] and enter the open-label section of the study [REDACTED]. If re-epithelialization is not achieved [REDACTED] a second dose of NEXAGON [REDACTED] will be applied. If re-epithelialization occurs [REDACTED], a final assessment of the epithelium durability will be performed [REDACTED].
 
Subjects will also exit the study if re-epithelialization is not achieved [REDACTED] in the open-label section of the study.
 
The MAXIMUM duration for study participation for a subject is [REDACTED]

-------------------------------	---

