6.3. Urine Pregnancy Test

Urine pregnancy tests will be performed on all female subjects of childbearing potential immediately PRIOR to randomization on Day 1 BEFORE application of investigational product. **The test must be confirmed as negative before randomization.** Another final pregnancy test will be performed when the subject re-epithelizes or when the subject exits the study due to non-healing of the PED or another reason.

In the event of pregnancy, the subject will be withdrawn from the study and the pregnancy will be followed up to term for safety evaluation.

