#### **13. Efficacy Analyses – Masked Portion of Study**

##### **13.1 Primary Efficacy Outcome Analysis**

The primary efficacy outcome will be the comparison of each dose of NEXAGON to Vehicle for the proportion of subjects with corneal epithelial recovery, defined as a cornea that re-epithelializes [REDACTED] of treatment and remains re-epithelialized [REDACTED] after initial re-epithelialization was first recorded (during the masked treatment portion of the study and assessed by the

Investigator). Subjects who discontinue the study early, or who have missing data resulting in the inability to conclude corneal epithelial recovery, will be considered as not having corneal epithelial recovery (missing data imputed as failure).

The number and proportion of subjects with corneal epithelial recovery will be summarized by treatment group and tested between treatment groups [REDACTED]

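### Sections 6.3 and 8.1.1 end observation together with product eligibility, so a healed eye can lose its durability assessment and be scored as a primary failure for a reason unrelated to the cornea

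*Protocol*

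**What the plan says.** **Withdrawal.** Protocol 8.1.1 states that "subjects WILL be withdrawn from the study, in consultation with the Medical Monitor and the Investigator" if a listed criterion is met. The visible criteria include pregnancy and this one: "A subject is significantly non-compliant with the requirements of the protocol". The list is not confined to the dosing period. Protocol 6.3 repeats the pregnancy rule without mentioning consultation: "In the event of pregnancy, the subject will be withdrawn from the study".

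**Timing of the test.** Protocol 6.3 requires a negative test before randomization on Day 1. It then says: "Another final pregnancy test will be performed when the subject re-epithelizes or when the subject exits the study".

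**What is still collected.** For the period after healing, 8.1.1 says: "Subjects who meet the criteria for premature withdrawal, during the Post-healing Follow-up Period will complete all the ophthalmic assessments of the visit" at which the criterion was identified, if possible. All premature exits also get a visit or telephone call for AEs and SAEs, 30 days after the last application. A pregnancy is followed to term for safety.

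**Product after healing.** For subjects who heal, the Protocol Synopsis (Study Periods/Duration) says: "No further investigational product will be applied". If the epithelium then breaks down, the subject becomes eligible for open-label salvage NEXAGON (Synopsis and Protocol 4.1).

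**Scoring.** Success requires the healed state to last for a redacted period (Protocol 3, SAP 2.1). SAP 13.1 scores as failures "Subjects who discontinue the study early, or who have missing data resulting in the inability to conclude corneal epithelial recovery", with no distinction by reason.

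**The concern.** Each rule is reasonable alone, but together they have an effect that was probably not intended. A cornea can heal and stay healed, yet count as a primary failure because the subject was removed for a reason unrelated to the eye. The missing outcome is one the study had already scheduled, and in the pregnancy case the sponsor remains in contact with the subject without collecting the eye result.

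At stake is misclassification of the primary endpoint. After healing, only successes in the making can be lost this way, so an arm that heals more has more eyes exposed to the rule.

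**Working it through.** There is no figure in the plan to reproduce. Recovery rates, arm sizes, power, alpha, allocation and the discontinuation rate are redacted in Protocol 10.1 and SAP 5. The check is a trace of the rules, followed by an illustration on assumed inputs.

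**Trace for a subject whose healing-day pregnancy test is positive**
1. Re-epithelialization is recorded and the test is done at that time (6.3).
2. The subject is withdrawn from the study (6.3, 8.1.1).
3. That visit's ophthalmic assessments are completed if possible (8.1.1). They show a healed eye but cannot show durability.
4. The remaining contact is for AEs and SAEs. It may be by telephone and is timed from the last application, not from healing.
5. Durability cannot be concluded, so SAP 13.1 scores failure.

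The same path applies to a subject judged significantly non-compliant after healing but before the durability visit. It does not apply when the criterion is found at the durability visit, because that visit's assessments are completed if possible.

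**Size under equal proportional loss.** Let p be an arm's true recovery rate and w the share of durably healed eyes lost. The observed rate is p(1-w), so the observed difference is (p1 - p2)(1-w). Assume p1 = 0.60, p2 = 0.20, n = 20 per arm and a two-sided 0.05 test. With pm the mean of the two observed rates and D their difference:

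power = Φ{[D - 1.96·√(2·pm(1-pm)/n)] / √([p1(1-p1) + p2(1-p2)]/n)}, with observed rates throughout.

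At w = 1% the observed rates are 0.594 and 0.198, D = 0.396 and pm = 0.396. The argument is (0.396 - 0.3031)/0.1414 = 0.657, so power is 74.4%.

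| w | Observed rates | Difference (points) | Power |
|---|---|---|---|
| 0 | 0.600 vs 0.200 | 40.0 | 75.2% |
| 1% | 0.594 vs 0.198 | 39.6 | 74.4% |
| 2% | 0.588 vs 0.196 | 39.2 | 73.6% |
| 5% | 0.570 vs 0.190 | 38.0 | 71.2% |

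**Plausible w for pregnancy alone.** The documents give no rate. If 20% to 50% of subjects were of childbearing potential and 0.5% to 2% of those conceived on study, w would run from 0.20 × 0.005 = 0.1% to 0.50 × 0.02 = 1.0%. The 40 points would become 39.96 to 39.6. The w = 5% row is an upper illustration without support in the documents.

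**Size of one eye.** One healed eye scored as failure lowers its arm's rate by 1/n: 6.7 points at n = 15, 5.0 at n = 20 and 3.3 at n = 30 (all assumed sizes).

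**The case against.** **Withdrawal after healing has a function.** A reader might infer that, since masked product has stopped, withdrawal only cancels the durability visit. The documents do not support that. A healed subject who stays and then breaks down becomes eligible for open-label NEXAGON, so withdrawal also ends access to further active product. This objection stands, and any change must leave that access untouched.

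**Few subjects can be affected.** Pregnancy, planned pregnancy and inadequate contraception are exclusions, and the Day 1 test must be negative. Non-compliance must be significant and is judged in consultation, while out-of-window visits are only recorded as deviations (4.1.1). Where non-compliance consists of missed visits, the durability outcome may be missing whatever the rule says. All this stands, and it limits the number affected without removing the path. The pregnancy rule has no threshold.

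**The direction is conservative.** The rule is the same in every arm, so equal loss dilutes the difference and does not favour NEXAGON. A reader might infer a bias from the fact that only healed eyes are exposed. The rule does not create one by itself: with equal w both rates shrink by the same factor. Bias needs w to differ between arms, and nothing visible says it would.

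**Handling may exist elsewhere.** The SAP contents list a separate exploratory analysis of re-epithelialization (14.2), so healing as such is probably reported. SAP 8.2 and 13.1.1 are redacted, and a sensitivity analysis may cover healed early exits. That could soften the effect but would not change the visible primary rule. The instruction in 8.1.1 to make every effort to perform the specified evaluations refers to the exit or same-visit evaluations and the safety contact, not to a later durability visit.

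**The sections do not contradict one another.** True. The point is what they do in combination, and it concerns observation, not clinical handling.

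**Conclusion.** The concern holds in a limited form. Followed as written, Protocol 6.3 and 8.1.1 with SAP 13.1 can score a durably healed eye as not recovered because the subject met a non-ocular withdrawal criterion before the durability visit. This rests on unredacted text.

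It should not be read as saying that every healed subject who becomes pregnant or non-compliant is counted as a failure, that non-compliance leads to automatic removal, or that 5% or more of healed eyes will be lost.

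On assumed rates of 60% and 20%, the loss is 0.4 points of difference at w = 1% and 2 points at w = 5%, always toward no effect if w is equal across arms. What makes it worth correcting is that a single eye matters in small arms (5 points at an assumed n = 20) and that the outcome could be collected at a visit already scheduled. It is a cheap improvement, not a threat to the trial's validity.

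**What to change.** Reconcile Protocol 6.3, Protocol 8.1.1 and SAP 13.1 as follows.

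- **Protocol 6.3 and 8.1.1:** distinguish the end of product eligibility from the end of observation. Eligibility for product, including open-label salvage, and all clinical handling remain as the sponsor decides, and this change does not alter them. A subject who meets one of these criteria after healing and still consents keeps the durability assessment already scheduled.
- **SAP 13.1:** score such a subject on the observed outcome. Reserve imputed failure for subjects with no assessment that allows recovery to be concluded. This also settles how to score a subject whose criterion is found at the durability visit itself.
- **Reporting:** in the disposition table, show subjects whose product eligibility ended separately from those whose observation ended.

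The cost is a wording amendment to two protocol sections, a sentence or two in the SAP, and one or a few scheduled observation visits for a small number of subjects. Some of those subjects will decline or not attend, and for them the failure rule still applies.
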